4.5 Disease Progression

If signs of progression are captured during study assessments, the patient and her medical oncologist (with the patient's permission) will be notified. The non-FDA approved research images cannot be assumed to be of clinical quality and, therefore, cannot substitute for a clinical evaluation. Subjects experiencing symptoms for which clinical imaging may be appropriate will be advised to see their treating physician.

5.0 EXPECTED RISKS/UNANTICIPATED PROBLEMS/SAFETY MONITORING

5.1 Assessment of Safety

One aspect of this study outside the usual standard of care is the potential complication associated with the application of higher intensity ultrasound than is used in routine diagnostic examinations. If applied for extended time periods, these high-intensity beams could cause tissue damage due to excessive heating. The FDA considers thermal increases less than 6 °C in soft tissue to be safe.³¹ Therefore, the beam sequences and timing of data acquisition used for this study will be designed to ensure that the cumulative temperature increase does not exceed 2°C, to further reduce patient risk and exposure. This is a research tool developed for academic purposes under the direction of [name] and is neither for commercial purposes nor under the direction of Siemens, the manufacturer of the ultrasound equipment.

The use of ARFI, VisR, and DDAI technology will build on experience from previous clinical studies conducted at UNC Chapel Hill ([name], PI). IRB review designated these research ultrasound technologies as minimal risk and qualifying for abbreviated IDE (exempt from FDA review). No adverse events occurred. Our proposed research study is similar in nature to these trials, but if the IRB review determines that FDA review for an IDE is required, then an IDE application will

be submitted at that time. Other acoustic radiation force (ARF)-based imaging methods are approved for clinical practice in Europe and in the United States. Overall, the potential risks to participants would be categorized as minimal. Participants will be informed of these risks at the time of informed consent.

Given that the mechanical stresses during ARFI imaging are significantly less than those routinely experienced during both physiological arterial pulsation³² and normal clinical evaluation by palpation, we believe this protocol poses no significant danger to the patient. Unexpected, unusual, or serious complications, or an unanticipated frequency of reactions during the course of the clinical investigation, will be reported immediately to the IRB.

The Principal Investigator, Co-Investigators, and Study Coordinators will have access to real time data on the rate of complications. If there is any increase in the rate of complications, we will review the entire protocol to seek solutions. Since the only addition to routine patient care associated with this study is ultrasound imaging that is believed to pose no significant risk to the patient, the chance of this happening is minimal. Any adverse events or unanticipated problems will be reported to the LCCC and the UNC IRB immediately.

5.2 Expected Risks (include Applicable Sections)

5.2.1 Patient Confidentiality

Identifiable information, which will be separated from research data, will be retained in a locked file cabinet, in a locked office, and password protected indefinitely. When the PI ([name]) determines that the identifiable information is no longer needed, it will be shredded (hard copy) and securely deleted (electronic). To achieve separation of identifiers from research data, all patient volunteers will be assigned unique study identification (ID) number at the time of enrollment. All acquired data will be labeled with the study ID number, and no personal information will be stored with the collected data. The master list linking study ID numbers to personal information will be secured by lock (hard-copy) and password (electronic copy) in [name] laboratory in the UNC-CH Joint Department of Biomedical Engineering. [name] computational work station is password-protected and locked in her research laboratory, so unauthorized personnel will not have access to personal identifiers. Any data transmission (by hard-copy or electronically) to authorized personnel will be stripped of any personal identifiers. The data will be tagged by the unique identifier assigned to the participant at the time of enrollment only. Electronically recorded data will be stored with study ID number only.

Except when required by law, study subjects will not be identified by name, social security number, address, telephone number, or any other direct personal identifier in study records disclosed outside of the University of North Carolina Hospitals, University of N.C. at Chapel Hill School of Medicine, and Departments of Radiology, Biomedical Engineering, and Oncology. No subject will be identified in any report or publication resulting from this study. All patient

volunteers will be assigned unique study identification (ID) number at the time of enrollment. All acquired data will be labeled with the study ID number, and no personal information will be stored with the collected data. The master list linking study ID numbers to personal information will be secured by lock (hard-copy) and password (electronic copy) in [name] laboratory in the UNC-CH Joint Department of Biomedical Engineering. [name] computational work station is password-protected and locked in her research laboratory, so unauthorized personnel will not have access to personal identifiers.

5.3 UNANTICIPATED CONCERNS

5.4 Unanticipated Adverse Device Effect (UADE)

The investigational device exemption (IDE) regulations define an unanticipated adverse device effect (UADE) as “any serious adverse effect on health or safety or any life-threatening problem or death caused by, or associated with, a device, if that effect, problem, or death was not previously identified in nature, severity, or degree of incidence in the investigational plan or application (including a supplementary plan or application), or any other unanticipated serious problem associated with a device that relates to the rights, safety, or welfare of subjects” (21 CFR 812.3(s)).

5.5 Unanticipated Problems (UP)

As defined by UNC's IRB, unanticipated problems involving risks to study subjects refers to any incident, experience, or outcome that:

- Is unexpected (in terms of nature, severity, or frequency) given (a) the research procedures that are described in the protocol-related documents, such as the IRB-approved research protocol and informed consent document; and (b) the characteristics of the subject population being studied;
- Is related or possibly related to a subject's participation in the research; and
- Suggests that the research places subjects or others at a greater risk of harm (including physical, psychological, economic, or social harm) related to the research than was previously known or recognized.

5.6 Reporting

5.6.1 UADEs

UADEs must be reported by the clinical investigator to the sponsor and the reviewing IRB, as described below:

For this device study, investigators are required to submit a report of a UADE to the FDA, the manufacturer of the device and the UNC IRB as soon as possible, but in no event later than 10 working days after the investigator first learns of the event (§ 812.150(a)(1)), using the MedWatch Form 3500A. Sponsors (LCCC) must immediately conduct an evaluation of a UADE and must report the results of

the evaluation to FDA, the UNC IRB, and participating investigators within 10 working days after the sponsor first receives notice of the effect (§§ 812.46(b), 812.150(b)(1)).

For this device study, we will submit a report of a UADE to the manufacturer and the IRB as soon as possible, but no later than 10 working days after the investigators first learn of the event.

5.7 UP

Any events that meet the criteria for “Unanticipated Problems” as defined by UNC’s IRB must be reported by the Study Coordinator using the IRB’s web-based reporting system.

Any unanticipated problem that occurs during the conduct of this study and that meets at least the criteria listed in section 5.6 must be reported to the UNC IRB using the IRB’s web-based reporting system.

5.8 Data and Safety Monitoring Plan

The Principal Investigator will provide continuous monitoring of patient safety in this trial with periodic reporting to the Data and Safety Monitoring Committee (DSMC).

Meetings/teleconferences will be held at a frequency dependent on study accrual, and in consultation with the study Biostatistician. These meetings will include the investigators as well as protocol nurses, clinical research associates, regulatory associates, data managers, biostatisticians, and any other relevant personnel the principal investigators may deem appropriate. At these meetings, the research team will discuss all issues relevant to study progress, including enrollment, safety, regulatory, data collection, etc.

The team will produce summaries or minutes of these meetings. These summaries will be available for inspection when requested by any of the regulatory bodies charged with the safety of human subjects and the integrity of data including, but not limited to, the oversight (Office of Human Research Ethics (OHRE) Biomedical IRB, the Oncology Protocol Review Committee (PRC) or the North Carolina TraCS Institute Data and Safety Monitoring Board (DSMB).

The UNC LCCC Data and Safety Monitoring Committee (DSMC) will review the study on a regular (quarterly to annually) basis, with the frequency of review based on risk and complexity as determined by the UNC Protocol Review Committee. The UNC PI will be responsible for submitting the following information for review: 1) safety and accrual data including the number of patients treated; 2) significant developments reported in the literature that may affect the safety of participants or the ethics of the study; 3) preliminary response data; and 4) summaries of team meetings that have occurred since the last report.

Findings of the DSMC review will be disseminated by memo to the UNC PI, PRC, and the UNC IRB and DSMB.

6.0 STATISTICAL CONSIDERATIONS

6.1 Study Design/Study Endpoints

For Aims #1 and #2, the ability of ultrasound biomarkers to discriminate binary outcomes (malignant/benign and responsive/unresponsive to treatment) will be analyzed using logistic regression. The area under the receiver operating characteristic curve (AUC) will be quantified, with separate models fit for each of the eight ultrasound biomarkers. Because most ultrasound biomarkers are continuous measures, the best-balanced cutpoints optimizing sensitivity and specificity will be calculated, using Youden's Index. Outcome discrimination by dual biomarkers will be analyzed in 28 separate models with combinations of any two ultrasound biomarkers. The combined benefit of ultrasound and mammography will be analyzed in 32 models, by adding a single mammography metric (lesion size, density, shape, or margins) to each of the eight ultrasound biomarker models. In Aim #2, the relationship between biomarker values and tumor size, biomarker values and change in tumor size, and change in biomarker values and change in tumor size will be analyzed by linear regression. These correlations will be analyzed in separate models for each of the eight ultrasound biomarkers, in models of dual ultrasound biomarkers, and in models combining mammography metrics with ultrasound biomarkers.

6.2 Sample Size and Accrual

A total of 80 participants will be recruited for this study. The study will be conducted in 40 women with diagnosed BIRADS-4 or -5 masses and in 40 women with malignant masses undergoing neoadjuvant chemotherapy.

We project 12 of the 40 women in our study will have malignant cancer, and 12 of 40 will have masses that do not respond to NAC. Given this, we expect 80% power to detect a minimum AUC of 0.70 (95% CI: 0.51 – 0.89). This is consistent with the diagnostic accuracy previously reported for malignancy detection by ultrasound biomarkers, which have ranged from AUC values of 0.67 to 0.99.^{5,10}

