6.3.1.3 What is the combined diagnostic accuracy of ultrasound metrics and mammography?

We will select ultrasound metrics with an AUC exceeding 0.75 in C.1.a-b, and their combined diagnostic accuracy with mammography measures (mass size, density, shape, and margins) will be analyzed in separate ROC curves.

6.3.1.4 Which cutpoints for ultrasound metrics detect malignancy with optimum sensitivity and specificity?

Best-balanced cutpoints from the highest performing ultrasound metrics in 6.3.1.1 will be derived from ROC curves, using Youden's Index. These cutpoints will be used to analyze the PPV.

6.3.2 Aim #2: Correlate ultrasound-derived stiffness, elasticity, viscosity, and anisotropy with response to treatment.

In 40 women with newly diagnosed invasive breast cancer who are scheduled to begin clinically indicated NAC, ARFI, VisR, and DDAI imaging will be performed (as described in Aim #1) at baseline, early within each chemotherapy type, and at the conclusion of each chemotherapy type over the course of treatment.

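### Section 6.2 claims 80% power at AUC 0.70, but 12 versus 28 women give about 51–55%; 80% is reached only near AUC 0.75–0.77 (two-sided 5%, null AUC 0.50)

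*Combined protocol and SAP*

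**What the plan says.** Section 6.2 (Sample Size and Accrual) sets the total: "A total of 80 participants will be recruited for this study". They form two cohorts of 40 with different outcomes. For Aim 1: "We project 12 of the 40 women in our study will have malignant cancer". For Aim 2: "12 of 40 will have masses that do not respond to NAC". Each aim therefore compares 12 women with 40 − 12 = 28.

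From these counts the section concludes: "we expect 80% power to detect a minimum AUC of 0.70 (95% CI: 0.51 – 0.89". It gives no significance level, sidedness, null AUC or method. It adds that published AUCs for such biomarkers run from 0.67 to 0.99.

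Section 6.3.1.3 later uses an observed AUC to choose metrics for the mammography analysis: "We will select ultrasound metrics with an AUC exceeding 0.75 in C.1.a-b". Sections 2.1.3, 2.2.8 and 6.3.2.8 use the same 0.75 threshold.

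**The concern.** The two halves of the power sentence do not agree. If the expected 95% interval at AUC 0.70 is "95% CI: 0.51 – 0.89", its lower limit barely clears 0.50. An observed AUC slightly below 0.70 would then give an interval that includes 0.50, and that happens almost half the time when the true AUC is 0.70. An interval placed like this goes with power a little above one half, not 80%.

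This sentence is the only sample-size argument for either aim. A metric that performs at the plan's own minimum AUC would often fail to separate from chance, and readers would take that result as coming from a well-powered study. AUCs near 0.70 are not remote: the range cited in 6.2 begins at 0.67.

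**Working it through.** **Inputs from 6.2.** m = 12, n = 28 per aim; A = 0.70; stated power 80%; stated 95% CI 0.51–0.89.

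**Assumptions, because the plan is silent.** Null AUC 0.50; two-sided 5%, which matches the 95% interval; no multiplicity adjustment and no dropout. A higher null, an adjustment or dropout would each lower the power.

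**1. Reproduce the printed interval (Hanley-McNeil).**
- A/(2 − A) = 0.70/1.30 = 0.5385, and 2A²/(1 + A) = 0.98/1.70 = 0.5765.
- Variance = [A(1 − A) + (m − 1)(0.5385 − A²) + (n − 1)(0.5765 − A²)]/(mn) = [0.21 + 11 × 0.0485 + 27 × 0.0865]/336 = 0.00916.
- SE = 0.0957, so 0.70 ± 1.96 × 0.0957 = 0.512 to 0.888.

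This matches the plan and points to 12 versus 28 and a two-sided 95% level as its inputs.

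**2. Power at AUC 0.70 from the same inputs.**
- SE under the null: √[(m + n + 1)/(12mn)] = √(41/4032) = 0.1008.
- Null SE in the test: Φ[(0.20 − 1.96 × 0.1008)/0.0957] = Φ(0.025) = 51.0%.
- Alternative SE throughout: Φ(0.20/0.0957 − 1.96) = Φ(0.13) = 55.2%.

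**3. AUC at which power reaches 80%.** Solving the same two expressions gives 0.772 (null SE) and 0.753 (alternative SE).

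**4. Other methods and readings for AUC 0.70.**

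| Reading | Power | 95% CI at 0.70 |
|---|---|---|
| 12 vs 28, two-sided 5%, Obuchowski variance | 51–56% | 0.51–0.89 |
| Same, equal-variance binormal variance | 51–60% | 0.52–0.88 |
| Same, t-test at d = √2 × Φ⁻¹(0.70) = 0.742 | 55.4% | – |
| Same, z-test at d = 0.742 | 57.5% | – |
| Same, simulated rank-sum (20,000 datasets) | 52.3% | – |
| Same, simulated DeLong (20,000 datasets) | 57.1% | – |
| 28 as the positive group, two-sided 5% | 51–65% | 0.53–0.87 |
| 12 vs 28, one-sided 5% | 64–69% in most methods | – |
| 28 as the positive group, one-sided 5% | 65–75% | 0.53–0.87 |
| 12 vs 28, one-sided 10%, Hanley-McNeil | 77–79% | 0.51–0.89 |
| Both cohorts pooled, 24 vs 56, two-sided 5% | 82–84% | 0.57–0.83 |

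**5. Alpha needed for 80%.**
- Null SE: z = (0.20 − 0.8416 × 0.0957)/0.1008 = 1.18, a two-sided alpha of about 0.24.
- Alternative SE: z = 2.09 − 0.84 = 1.25, about 0.21.

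**6. Sample size for 80% at AUC 0.70.** With 30% in the smaller group, the null-SE formula needs about 77 women per aim (about 23 versus 54).

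**7. The 0.75 threshold.** If the true AUC is 0.70, the chance of observing more than 0.75 is about 1 − Φ(0.05/0.0957) = 1 − Φ(0.52) = 30%; simulation gives 29–30%.

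**The case against.** The best defence has four parts.

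- **Unstated inputs.** The plan gives no alpha, sidedness or null, so 51–55% depends on assumptions. This stands, and the figure must carry them. Two-sided 5% is nevertheless the natural reading beside a 95% interval.
- **A wider range.** Other variance formulas reach about 60%. In Aim 2 the target outcome is a positive response, so the 28 responders may be the positive group, which gives up to 65% two-sided. This is fair, but none of these values approaches 80%, and putting the 28 first no longer reproduces the printed interval.
- **Readings near 80%.** A one-sided 10% test comes close with 12 versus 28, but the plan mentions no such level. Pooling all 80 women exceeds 80%, but it implies a narrower interval than the one printed and mixes malignancy with treatment response. How the 80% arose is unknown. One possibility that fits the interval is that the smallest significant AUC, 0.5 + 1.96 × 0.1008 = 0.698, was labelled as the AUC detectable with 80% power.
- **Limited consequence.** Section 1.4 calls the study exploratory, and section 6 sets no formal test or success criterion on the AUC; the 0.75 rule only selects metrics for the mammography models. This limits the harm and argues against enlarging the study. It does not make the printed power correct.

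**Conclusion.** The concern holds: the power statement in 6.2 is wrong as written. With 12 versus 28 women, a null AUC of 0.50 and a two-sided 5% level, power at AUC 0.70 is 51–55% by Hanley-McNeil, the method that reproduces the plan's own interval. The claim is therefore 25 to 29 percentage points too high. Power of 80% is reached at an AUC of about 0.75–0.77. Other accepted methods widen the power range to about 51–60%, or to 65% with responders as the positive group. One-sided 5% gives at most 75%. No reading at a conventional 5% level with 40 women per aim supports the stated figure. The printed confidence interval is correct and can be kept.

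**What to change.** Keep 40 women per aim and replace the power sentence in 6.2. Possible wording:

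> Assuming 12 and 28 women in the two outcome groups of each aim, a null AUC of 0.50 and a two-sided 5% level without multiplicity adjustment, power is about 51–55% for a true AUC of 0.70 and reaches 80% at a true AUC of about 0.75–0.77. At an AUC of 0.70 the expected 95% confidence interval is 0.51–0.89. The sample size is justified by this precision for an exploratory study.

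If a different level or sidedness was intended, state it and recompute the figures. If 80% power at AUC 0.70 is a real requirement, the plan should acknowledge that it needs about 77 women per aim.

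The cost is one sentence and a less favourable figure. Enrolment, imaging and analyses do not change.

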6.3 Data Analysis Plans

6.3.1 Aim #1: Correlate ultrasound-derived stiffness, elasticity, viscosity, and anisotropy to malignancy.

In vivo ARFI, VisR, and DDAI imaging will be performed in 40 women with a breast mass with a BIRADS breast assessment categories of -4a, 4b, 4c, or -5 rating after diagnostic workup. First, the transducer will be placed lightly above the suspicious mass, just to the point of skin contact, to avoid pre-compression during imaging.¹⁵ The suspicious mass will be positioned at 10 to 40 mm in axial depth, with standoff used if needed to achieve the desired axial position. Second,

the position of the transducer will be rotated through 90° in steps of 30° to identify the transducer position yielding maximum ARFI peak displacement in the mass. The transducer will be stabilized in this position, with light skin contact, by the sonographer or by using a stereotactic clamp. Third, ARFI and VisR data will be acquired in immediate succession. Fourth, the transducer will be rotated 90°, re-stabilized by the sonographer or by using the stereotactic clamp, and ARFI and VisR data will be acquired in the new transducer position to enable DDAI analysis. Finally, the evaluated mass will undergo clinically indicated biopsy with histological evaluation to determine if it is benign or malignant.

The ultrasound data will be processed to calculate the following outcome metrics: peak displacement (PD), displacement at a given time (TD) for ARFI; τ , relative elasticity (RE), relative viscosity (RV), and tissue mass (TM) for VisR; ratio of ARFI PD and ratio of VisR RE values at 90° versus 0° transducer orientations for DDAI. These eight outcome metrics, alone and in combinations, will be statistically correlated with biopsy finding of malignant or benign.

6.3.1.1 Which of the 8 ultrasound metrics best detects malignancy?

The diagnostic accuracy of each ultrasound metric will be analyzed by constructing separate receiver operating characteristic (ROC) curves.

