2.0 STUDY OBJECTIVES

The purpose of this study is to evaluate *in vivo* the diagnostic relevance of ultrasound-derived stiffness, elasticity, viscosity, and anisotropy metrics for breast lesion malignancy and response to treatment.

2.1 Aim #1: Quantify the ability of ultrasound-derived stiffness, elasticity, viscosity, and anisotropy to detect malignancy.

In vivo ARFI, VisR, and DDAI imaging will be performed in 40 women with a breast mass with a BIRADS breast assessment categories of -4a, 4b, 4c, or -5 rating after diagnostic workup. First, the transducer will be placed lightly above the suspicious mass, just to the point of skin contact, to avoid pre-compression during imaging.¹⁵ The suspicious mass will be positioned at 10 to 40 mm in axial depth, with standoff used if needed to achieve the desired axial position. Second, the position of the transducer will be rotated through 90° in steps of 30° to identify the transducer position yielding maximum ARFI peak displacement in the mass. The transducer will be stabilized in this position, with light skin contact, by the sonographer or by using a stereotactic clamp. Third, ARFI and VisR data will be acquired in immediate succession. Fourth, the transducer will be rotated 90°, re-stabilized by the sonographer or by using the stereotactic clamp, and ARFI and VisR data will be acquired in the new transducer position to enable DDAI analysis. Finally, the evaluated mass will undergo clinically indicated biopsy with histological evaluation to determine if it is benign or malignant.

The ultrasound data will be processed to calculate the following outcome metrics: peak displacement (PD), displacement at a given time (TD) for ARFI; τ , relative elasticity (RE), relative viscosity (RV), and tissue mass (TM) for VisR; ratio of ARFI PD and ratio of VisR RE values at 90° versus 0° transducer orientations for DDAI. These eight outcome metrics, alone and in combinations, will be statistically correlated with biopsy finding of malignant or benign.

2.1.1 Determine which of the 8 ultrasound metrics best detects malignancy.

We will statistically evaluate all eight ultrasound outcome metrics independently to determine which metric best detects malignant finding.

2.1.2 Determine the combined diagnostic accuracy of any 2 ultrasound metrics.

We will systematically combine all possible groupings of two ultrasound outcome metrics. We will then determine which grouping of metrics best detects malignant finding.

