6.3.2.1 Which baseline ultrasound metric best predicts positive response to NAC?

Response to NAC will be dichotomized into a yes/no response according to the RECIST guidelines, and the predictive ability of each baseline ultrasound metric will be analyzed by constructing separate ROC curves.

6.3.2.2 Which baseline ultrasound metric correlates most strongly with absolute reduction in tumor size (diameter, area, volume)?

The relationship between ultrasound metric values at baseline and absolute change in tumor size from baseline to end of chemotherapy type will be visualized by scatterplots. If the relationship appears linear and monotonic, the correlation will be assessed by Pearson regression.

6.3.2.3 What is the combined ability of any 2 baseline ultrasound metrics for prediction of positive response to NAC?

With response to NAC dichotomized into a yes/no response, the combined predictive ability will be analyzed by constructing separate ROC curves for combinations of any 2 ultrasound metrics.

6.3.2.4 Do serial changes in ultrasound metrics correlate with reduction in tumor size following NAC?

The relationships between serial changes in ultrasound metrics and tumor size will be visualized by scatterplots. If monotonic and linear, the correlation between serial change in ultrasound metrics and change in tumor size (area) will be analyzed by Pearson regression. Assessments of serial change will be made at 3 intervals per chemotherapy type: baseline, early chemotherapy type treatment, and end of chemotherapy type treatment.

6.3.2.5 Serial change in which of the 8 ultrasound metrics best predicts positive response to NAC?

Response to NAC will be dichotomized into a yes/no response, and the predictive ability of serial change in each ultrasound metric from 0-6 weeks will be analyzed by constructing separate ROC curves.

6.3.2.6 Do combinations of changes over time in any ultrasound outcome metrics correlate with reduction in tumor size following NAC?

Assuming linear relationships exists between serial change in ultrasound metrics and serial change in tumor size following NAC, multiple linear regression models will be constructed for each of the 8 ultrasound metrics. The model outcome will be change in tumor size, and model predictors will be serial change in any 2 ultrasound metrics.

6.3.2.7 Which combinations of serial change for any 2 ultrasound metrics best predicts positive response to NAC?

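### The plan asks which of eight ultrasound metrics is best, but builds only separate ROC curves on the same women, with no paired AUC difference and no measure of how uncertain the ranking is

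*Combined protocol and SAP*

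**What the plan says.** Objective 2.1.1 is comparative. The eight metrics are each evaluated "to determine which metric best detects malignant finding". The matching analysis in section 6.3.1.1 reads: "The diagnostic accuracy of each ultrasound metric will be analyzed by constructing separate receiver operating characteristic (ROC) curves". For Aim 2, objective 2.2.1 asks which baseline metric best predicts response, and section 6.3.2.1 answers that "the predictive ability of each baseline ultrasound metric will be analyzed by constructing separate ROC curves". Section 6.3.2.5 takes the same approach to serial change, and section 6.1 fits a separate logistic model for each biomarker.

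Section 6.2 sizes the study for one AUC at a time. It states "We project 12 of the 40 women in our study will have malignant cancer", makes the same 12-of-40 projection for non-response to chemotherapy, and concludes "we expect 80% power to detect a minimum AUC of 0.70", with a 95% interval of 0.51 to 0.89. It describes published AUCs for malignancy detection "which have ranged from AUC values of 0.67 to 0.99".

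No section gives a method for the difference between two AUCs, an interval for such a difference, a measure of rank uncertainty, or a rule for near-ties. The cutpoint steps (2.1.4 and 6.3.1.4; 2.2.9 and 6.3.2.9) then take forward the top-performing metrics. Section 1.4 calls the study exploratory.

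**The concern.** Eight AUCs measured on the same lesions are correlated. How far apart two of them are depends on that correlation, and eight separate curves or intervals do not show it. Some metric will always come first in the sample, even if all eight are equally good, and following the plan literally would report it as best.

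This differs from optimism in the leader's own AUC. Even if every AUC were unbiased, the metric in first place would not have been shown to beat the one in second. At stake is the answer to three stated objectives and, in part, the choice of metrics that receive cutpoints and a PPV.

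**Working it through.** **Inputs from the documents.** Aim 1 has 40 women, 12 of them projected malignant, leaving 40 − 12 = 28 benign. Aim 2 has the same projected split (12 non-responders, 28 responders). There are eight metrics, hence 8 × 7 / 2 = 28 pairwise contrasts.

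**Assumed, because the documents do not say.** Metrics are normal within each outcome class. The between-metric correlation is 0 to 0.8, with 0.9 and 0.95 also tried.

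**The plan's own figure.** The Hanley-McNeil variance is [A(1−A) + (m−1)(Q₁−A²) + (n−1)(Q₂−A²)] / mn, with Q₁ = A/(2−A) and Q₂ = 2A²/(1+A). For A = 0.70, m = 12 and n = 28, Q₁ = 0.538 and Q₂ = 0.576. The variance is (0.210 + 0.533 + 2.335)/336 = 0.00916, so SE = 0.0957. The interval is 0.70 ± 1.96 × 0.0957 = 0.512 to 0.888, which reproduces the printed one.

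The 80% power does not reproduce at alpha 0.05 against a null of 0.50. It comes to 51-56% two-sided and 64-68% one-sided, and only one-sided 0.10 comes close (77-79%). Alpha is not stated. That is a separate matter: this point rests on the standard error, which the printed interval confirms.

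**Precision and ranking.** Eight equally correlated metrics were simulated with 12 and 28 women:

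| Between-metric correlation | 0 | 0.5 | 0.8 |
|---|---|---|---|
| SD of a paired AUC difference | 0.12 | 0.09 | 0.06 |
| 95% half-width (1.96 × unrounded SD) | 0.23 | 0.17 | 0.12 |
| True best 0.75, seven at 0.70: best ranks first | 25% | 31% | 46% |
| True best 0.80, seven at 0.70: best ranks first | 44% | 57% | 82% |

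If all eight are truly 0.70, the observed top and bottom still differ on average by 0.19 (correlation 0.5) or about 0.12 (0.8).

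**Paired DeLong test, two-sided 0.05, two metrics.** For a true gap of 0.05, power is 8-10% at correlation 0 to 0.7 and 16-18% at 0.9. For a gap of 0.10, it is 15-31% and 55-60% respectively, rising to 78-80% at 0.95, before any allowance for multiple comparisons.

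**Where the problem shrinks.**
- Spread runners-up: with a best of 0.80 and the others between 0.70 and 0.55, the best ranks first in about 65-67%, 78-81% and 88-90% of trials at correlation 0, 0.5 and 0.7.
- High correlation: with 0.80 against seven at 0.70, the best ranks first in about 95% at correlation 0.9. With 0.75 against seven at 0.70, it is still only 58-62%.
- Large gap: with 0.90 against seven at 0.70, the best ranks first in 97.5% at correlation 0.5.

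**The case against.** The best defence has four parts.

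- The study is labelled exploratory and imposes nothing beyond imaging. Taking the highest AUC as a lead for later work is ordinary practice, and a paired test would not change which metric comes first.
- A wrong pick costs little when the gaps are small. At correlation 0.5 the expected loss in true AUC is about 0.69 × 0.05 = 0.03 in the 0.75 case and 0.43 × 0.10 = 0.04 in the 0.80 case.
- Seven exactly tied runners-up is the hardest case for ranking. The AUC range cited in section 6.2, 0.67 to 0.99, leaves room for larger gaps.
- The cutpoint steps take metrics in the plural, and the mammography step selects on AUC above 0.75. That is a threshold, not a ranking.

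All four are correct as facts, and they limit the size of the point. They also rule out a stronger reading that a reader might infer: that gaps of 0.05 to 0.10 can never be separated in 40 women, that the leader will usually be the wrong metric, or that everything downstream hangs on one winner. The correlation that decides the first two is not in the documents, and the third does not match the text of the cutpoint and mammography steps.

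The defence does not supply the missing step. Naming the best metric is a stated objective, and an exploratory study still has to show how firm its ranking is.

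**Conclusion.** The point holds in this limited form. The plan poses a comparative question three times and gives no analysis that compares, so a claim that one metric is best would be unsupported whatever the size of the true gap. How often the leader would be the wrong metric depends on assumptions. With 12 and 28 women, correlation 0 to 0.8 and seven tied runners-up at 0.70, the wrong metric leads in about 54-75% of trials when the best is 0.75, and in about 18-56% when it is 0.80. These are upper-end figures for those gaps.

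The change is worth making because it is cheap and bears directly on stated objectives. It does not call the study's conduct into question.

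**What to change.** In 6.3.1.1, 6.3.2.1 and 6.3.2.5, add a paired bootstrap that resamples women within outcome class and keeps each woman's eight metrics together. For every metric, report the AUC difference from the top-ranked metric and the share of resamples in which it ranks first. Describe the leader as having the highest observed AUC.

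Do not claim that it is better than another metric unless a simultaneous interval excludes zero. The interval should be max-type or multiplicity-adjusted, and must allow for the reference having been chosen from the data; covering all 28 pairwise contrasts does this. If a set of metrics not separable from the leader is reported or carried to the cutpoint steps, define it by the same intervals.

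Ordinary 95% intervals would not do. With eight truly equal metrics, they declared at least one inferior to the leader in roughly 48-64% of simulated trials. Nor should a single winner be required. Insisting that the leader's ordinary intervals exclude zero against all seven others named one metric in only about 1-8% of trials with 0.80 against seven at 0.70, and simultaneous intervals would be stricter still.

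The cost is SAP wording and a little more analysis, with no extra women or measurements. The usual result will be a set of candidate metrics instead of one winner, which suits a study labelled exploratory.
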